## 16.4 Appendix IV: Columbia-Suicide Severity Rating Scale (C-SSRS) Since Last Visit

SUICIDAL IDEATION	
Ask questions 1 and 2. If both are negative, proceed to "Suicidal Behavior" section. If the answer to question 2 is "yes", ask questions 3, 4 and 5. If the answer to question 1 and/or 2 is "yes", complete "Intensity of Ideation" section below.	Since Last Visit

1. Wish to be Dead
 
Subject endorses thoughts about a wish to be dead or not alive anymore, or wish to fall asleep and not wake up.
 
Have you wished you were dead or wished you could go to sleep and not wake up?
 
If yes, describe:
	
Yes
 
No
 
 

2. Non-Specific Active Suicidal Thoughts
 
General, non-specific thoughts of wanting to end one's life/commit suicide (e.g., "I've thought about killing myself") without thoughts of ways to kill oneself/associated methods, intent, or plan during the assessment period.
 
Have you actually had any thoughts of killing yourself?
 
If yes, describe:
	
Yes
 
No
 
 

3. Active Suicidal Ideation with Any Methods (Not Plan) without Intent to Act
 
Subject endorses thoughts of suicide and has thought of at least one method during the assessment period. This is different than a specific plan with time, place or method details worked out (e.g., thought of method to kill self but not a specific plan). Includes person who would say, "I thought about taking an overdose but I never made a specific plan as to when, where or how I would actually do it...and I would never go through with it."
 
Have you been thinking about how you might do this?
 
If yes, describe:
	
Yes
 
No
 
 

4. Active Suicidal Ideation with Some Intent to Act, without Specific Plan
 
Active suicidal thoughts of killing oneself and subject reports having some intent to act on such thoughts, as opposed to "I have the thoughts but I definitely will not do anything about them."
 
Have you had these thoughts and had some intention of acting on them?
 
If yes, describe:
	
Yes
 
No
 
 


5. Active Suicidal Ideation with Specific Plan and Intent
 
Thoughts of killing oneself with details of plan fully or partially worked out and subject has some intent to carry it out.
 
Have you started to work out or worked out the details of how to kill yourself?
 
Do you intend to carry out this plan?
 
If yes, describe:
	
Yes
 
No
 
 

INTENSITY OF IDEATION	

The following features should be rated with respect to the most severe type of ideation (i.e., 1-5 from above, with 1 being the least severe and 5 being the most severe).
 
Most Severe Ideation: _____
 
Type # (1-5) Description of Ideation
	Most Severe

Frequency
 
How many times have you had these thoughts?
 
(1) Less than once a week (2) Once a week (3) 2-5 times in week (4) Daily or almost daily (5) Many times each day
	_____

Duration
 
When you have the thoughts, how long do they last?
 
(1) Fleeting - few seconds or minutes (4) 4-8 hours/most of day
 
(2) Less than 1 hour/some of the time (5) More than 8 hours/persistent or continuous
 
(3) 1-4 hours/a lot of time
	_____

Controllability
 
Could/can you stop thinking about killing yourself or wanting to die if you want to?
 
(1) Easily able to control thoughts (4) Can control thoughts with a lot of difficulty
 
(2) Can control thoughts with little difficulty (5) Unable to control thoughts
 
(3) Can control thoughts with some difficulty (0) Does not attempt to control thoughts
	_____

Deterrents
 
Are there things - anyone or anything (e.g., family, religion, pain of death) - that stopped you from wanting to die or acting on thoughts of committing suicide?
 
(1) Deterrents definitely stopped you from attempting suicide (4) Deterrents most likely did not stop you
 
(2) Deterrents probably stopped you (5) Deterrents definitely did not stop you
 
(3) Uncertain that deterrents stopped you (0) Does not apply
	_____

Reasons for Ideation
 
What sort of reasons did you have for thinking about wanting to die or killing yourself? Was it to end the pain or stop the way you were feeling (in other words you couldn't go on living with this pain or how you were feeling) or was it to get attention, revenge or a reaction from others? Or both?
 
(1) Completely to get attention, revenge or a reaction from others (4) Mostly to end or stop the pain (you couldn't go on
 
(2) Mostly to get attention, revenge or a reaction from others living with the pain or how you were feeling)
 
(3) Equally to get attention, revenge or a reaction from others (5) Completely to end or stop the pain (you couldn't go on and to end/stop the pain living with the pain or how you were feeling)
 
(0) Does not apply
	_____

Information obtained from: <http://www.cssrs.columbia.edu/>

SUICIDAL BEHAVIOR	Since Last Visit
(Check all that apply, so long as these are separate events; must ask about all types)	


Actual Attempt:  A potentially self-injurious act committed with at least some wish to die, as a result of act. Behavior was in part thought of as method to kill oneself. Intent does not have to be 100%. If there is any intent/desire to die associated with the act, then it can be considered an actual suicide attempt. There does not have to be any injury or harm, just the potential for injury or harm. If person pulls trigger while gun is in mouth but gun is broken so no injury results, this is considered an attempt.  Inferring Intent: Even if an individual denies intent/wish to die, it may be inferred clinically from the behavior or circumstances. For example, a highly lethal act that is clearly not an accident so no other intent but suicide can be inferred (e.g., gunshot to head, jumping from window of a high floor/story). Also, if someone denies intent to die, but they thought that what they did could be lethal, intent may be inferred.  Have you made a suicide attempt?  Have you done anything to harm yourself?  Have you done anything dangerous where you could have died?  What did you do?  Did you _____ as a way to end your life?  Did you want to die (even a little) when you _____?  Were you trying to end your life when you _____?  Or did you think it was possible you could have died from _____?  Or did you do it purely for other reasons / without ANY intention of killing yourself (like to relieve stress, feel better, get sympathy, or get something else to happen)? (Self-Injurious Behavior without suicidal intent)  If yes, describe:
 
Has subject engaged in Non-Suicidal Self-Injurious Behavior?
	
Yes No   
 
Total # of Attempts  _____
 
Yes No   


Interrupted Attempt:  When the person is interrupted (by an outside circumstance) from starting the potentially self-injurious act (if not for that, actual attempt would have occurred).  Overdose: Person has pills in hand but is stopped from ingesting. Once they ingest any pills, this becomes an attempt rather than an interrupted attempt. Shooting: Person has gun pointed toward self, gun is taken away by someone else, or is somehow prevented from pulling trigger. Once they pull the trigger, even if the gun fails to fire, it is an attempt. Jumping: Person is poised to jump, is grabbed and taken down from ledge. Hanging: Person has noose around neck but has not yet started to hang - is stopped from doing so.  Has there been a time when you started to do something to end your life but someone or something stopped you before you actually did anything?  If yes, describe:
	
Yes No   
 
Total # of interrupted  _____

Aborted Attempt:  When person begins to take steps toward making a suicide attempt, but stops themselves before they actually have engaged in any self-destructive behavior. Examples are similar to interrupted attempts, except that the individual stops him/herself, instead of being stopped by something else.  Has there been a time when you started to do something to try to end your life but you stopped yourself before you actually did anything?  If yes, describe:
	
Yes No   
 
Total # of aborted  _____

Preparatory Acts or Behavior:  Acts or preparation towards imminently making a suicide attempt. This can include anything beyond a verbalization or thought, such as assembling a specific method (e.g., buying pills, purchasing a gun) or preparing for one's death by suicide (e.g., giving things away, writing a suicide note).  Have you taken any steps towards making a suicide attempt or preparing to kill yourself (such as collecting pills, getting a gun, giving valuables away or writing a suicide note)?  If yes, describe:
	
Yes No   

Suicidal Behavior:  Suicidal behavior was present during the assessment period?
	
Yes No   

Suicide:
	
Yes No   

Answer for Actual Attempts Only
	
Most Lethal Attempt Date:


Actual Lethality/Medical Damage:
 
0. No physical damage or very minor physical damage (e.g., surface scratches).
 
1. Minor physical damage (e.g., lethargic speech; first-degree burns; mild bleeding; sprains).
 
2. Moderate physical damage; medical attention needed (e.g., conscious but sleepy, somewhat responsive; second-degree burns; bleeding of major vessel).
 
3. Moderately severe physical damage; medical hospitalization and likely intensive care required (e.g., comatose with reflexes intact; third-degree burns less than 20% of body; extensive blood loss but can recover; major fractures).
 
4. Severe physical damage; medical hospitalization with intensive care required (e.g., comatose without reflexes; third-degree burns over 20% of body; extensive blood loss with unstable vital signs; major damage to a vital area).
 
5. Death
	
Enter Code
 
_____

Potential Lethality: Only Answer if Actual Lethality=0
 
Likely lethality of actual attempt if no medical damage (the following examples, while having no actual medical damage, had potential for very serious lethality: put gun in mouth and pulled the trigger but gun fails to fire so no medical damage; laying on train tracks with oncoming train but pulled away before run over).
 
0 = Behavior not likely to result in injury
 
1 = Behavior likely to result in injury but not likely to cause death
 
2 = Behavior likely to result in death despite available medical care
	
Enter Code
 
_____

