### 13.4 Secondary Analyses

We will use the same shared-baseline mixed model analysis to test other continuous secondary efficacy outcomes (additional TMS parameters, NCS parameters, ALSFRS-R, and SVC). MEP threshold, the key secondary outcome, will be tested prior to and separate from all other secondary efficacy outcomes. We will compare trajectories in TMS and NCS parameters between ALS and matched healthy control subjects in an augmented model with the addition of fixed effects for patient group (2 levels: ALS and healthy controls) and patient group x visit interactions (9 levels: 6 visits for ALS patients and 3 for matched healthy controls) and separate patient-level variance-covariance and residual variance estimates by patient group. Comparisons between matched healthy controls and ALS patients will be estimated using linear contrasts.

Safety and tolerability will be compared across treatments by log-rank test of time to first SAE, time to death, and time to dose discontinuation and by negative binomial regression of overall SAE and AE rates. The proportion of participants experiencing each MedDRA-classified AE will be compared across treatment groups by Fisher's exact test. Treatment-dependent differences in suicidality will be estimated from C-SSRS total scores analyzed using the same shared-baseline mixed model used for the primary analysis.

Serum PK estimates will be obtained for  $C_{max}$  and time to peak concentration.

Associations between firing rate of iPSC-derived motor neurons and baseline *in vivo* neurophysiological excitability indices will be compared within and between ALS and healthy control subjects by linear regression with *in vivo* paired pulse SICI as the dependent variable and

*in vitro*-firing rate, disease status and their interaction as predictors. A change-point model will be explored with a break at each participant's *in vitro*-estimated EC50 for blocking motor neuron spontaneous action potential firing by ezogabine. Spontaneous firing rate of the *in vitro*-derived motor neurons and *in vitro*-estimated EC50 for blocking motor neuron spontaneous action potential firing by ezogabine will be considered as moderators of treatment efficacy in tests of neurophysiological and clinical response by augmenting the shared-baseline mixed models with fixed effects for iPSC parameters, the two-way interaction with visit, and the three-way interaction with treatment group and post-baseline visit.

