### 3.9.2 Suicidality

The proportion of participants who report any post-baseline suicidal ideation or any post-baseline suicidal behavior will be summarized by treatment group. Suicidal behaviors will include: actual attempts, non-suicidal self-injurious behavior, interrupted attempts, aborted attempts, preparatory acts or behaviors, and completed suicide. The most severe ideation, maximal frequency, maximal duration, minimal controllability, minimal deterrents, maximal reasons for ideation, maximal actual lethality or medical damage, and maximal potential lethality will be summarized as means, standard deviations, medians, and ranges by treatment group.

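### SAP 3.9.2 averages C-SSRS severity items that the form records only for participants with ideation or an attempt, so the arm means can mislead about severity

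*Protocol*

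**What the plan says.** **The form (Protocol Appendix IV).** Ideation questions 1 and 2 are put to everyone. For a participant who denies both, the instruction is: "If both are negative, proceed to 'Suicidal Behavior' section". Otherwise, "If the answer to question 1 and/or 2 is 'yes', complete 'Intensity of Ideation' section below". Ideation type is graded "with 1 being the least severe and 5 being the most severe", with no level for no ideation. On the intensity items, "The following features should be rated with respect to the most severe type of ideation". Three of them (controllability, deterrents, reasons) also have a code 0 with its own meaning; for controllability it is "0) Does not attempt to control thoughts". Actual lethality is answered for actual attempts only, and the next item is restricted further: "Potential Lethality: Only Answer if Actual Lethality=0".

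**The SAP.** Section 3.9.2 first gives, by treatment group, the proportion of participants with any post-baseline ideation or behaviour. It then takes each participant's most severe ideation, extreme intensity codes, and maximal actual and potential lethality. The sentence that lists these items ends: "maximal potential lethality will be summarized as means, standard deviations, medians, and ranges by treatment group". It does not say over whom, or what happens to participants with nothing recorded. Section 3.2.2 sets the ST sample as denominator, but for proportions only. Section 3.1.2 puts the number of subjects and the range beside every mean.

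**The protocol's own analysis.** Section 13.4 has a different plan: "Treatment-dependent differences in suicidality will be estimated from C-SSRS total scores", using the mixed model of the primary analysis. SAP section 1 makes the SAP authoritative on analysis, and the SAP does not carry that model forward.

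**The concern.** Whether a participant has an intensity score depends on whether that participant developed ideation, which is part of the safety outcome. A mean over recorded scores therefore compares two groups that randomisation did not form. If the drug provokes mild ideation in people who would otherwise have had none, those people enter the active arm's mean with low scores and pull it down. More harm then produces a lower mean severity.

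Suicidality is a named safety objective (SAP 2.2), and Protocol 2.3.1.1 cites roughly a doubling of suicide risk in pooled analyses of antiepileptic drugs. The incidence proportion does not separate a passive wish to be dead from a plan with intent, and no count by ideation category is planned. The arm means are the only between-arm summary of how severe ideation typically was, so they should be readable.

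**Working it through.** The documents give no expected ideation rate, C-SSRS mean or power statement, so there is no plan figure to reproduce. The check asks which way each summary moves when mild cases are added to one arm.

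**Inputs.** 40 per arm (SAP 3.4). Ideation types 1 to 5 and the skip rules come from Appendix IV. All counts of participants with ideation are assumed.

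**Main illustration.** Placebo: 2 participants, both type 4. Ezogabine: the same 2, plus three new type 1 and three new type 2.

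- Recorded scores only: placebo (4 + 4)/2 = 4.0; ezogabine (4 + 4 + 3×1 + 3×2)/8 = 17/8 = 2.125. The ezogabine scores are 1, 1, 1, 2, 2, 2, 4, 4, so the medians are 4 and 2.
- All 40, with no ideation set to 0: 8/40 = 0.20 and 17/40 = 0.425.
- Any ideation: 2/40 = 5% and 8/40 = 20%.

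The recorded-only mean moves against the other two summaries.

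**Range.** Let placebo have b participants at type s, and ezogabine the same b plus m more at type 1. The recorded-only means are s and (bs + m)/(b + m). The means over all 40 are bs/40 and (bs + m)/40. The proportions are b/40 and (b + m)/40. Each cell gives placebo against ezogabine.

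| b, s, m | Recorded only | All 40, none = 0 | Any ideation |
|---|---|---|---|
| 2, 4, 1 | 4.00 vs 3.00 | 0.20 vs 0.225 | 5% vs 7.5% |
| 2, 4, 6 | 4.00 vs 1.75 | 0.20 vs 0.35 | 5% vs 20% |
| 2, 4, 10 | 4.00 vs 1.50 | 0.20 vs 0.45 | 5% vs 30% |
| 1, 4, 6 | 4.00 vs 1.43 | 0.10 vs 0.25 | 2.5% vs 17.5% |
| 4, 4, 6 | 4.00 vs 2.20 | 0.40 vs 0.55 | 10% vs 25% |
| 2, 5, 6 | 5.00 vs 2.00 | 0.25 vs 0.40 | 5% vs 20% |
| 2, 2, 6 | 2.00 vs 1.25 | 0.10 vs 0.25 | 5% vs 20% |
| 2, 1, 6 | 1.00 vs 1.00 | 0.05 vs 0.20 | 5% vs 20% |

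The recorded-only mean falls in every row except the last, where the existing cases are as mild as the new ones. With no placebo ideation its mean is undefined. The other two columns rise throughout.

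**Can blanks simply be set to 0?** For ideation type, yes: a participant who denies questions 1 and 2 is known to have no ideation. For controllability, deterrents and reasons, no: 0 already means that no control is attempted, or that the item does not apply. The lethality scales also use 0 for a real state, an attempt with little or no damage or with injury unlikely.

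**Potential lethality.** Suppose both arms have two uninjured attempts scored 1 and 2, and one arm has two further attempts with actual lethality 3. Mean potential lethality is (1 + 2)/2 = 1.5 in both arms. Mean actual lethality among attempters is 0 against (0 + 0 + 3 + 3)/4 = 1.5. The added harm shows only in the second item.

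**Direction of coding.** Higher controllability and deterrents codes describe a worse state. SAP 3.2.2 asks for the maximum of these items; SAP 3.9.2 asks for the minimal. The two agree only if minimal means the worst state and not the lowest code.

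**The case against.** The best defence is that the tables do not stand alone. The opening sentence of SAP 3.9.2 reports the incidence of ideation and behaviour by arm, and 3.2.2 takes such proportions over the whole ST sample. In the illustration that line reads 5% against 20%. Beside the means, n would read 2 against 8, and both ranges would reach 4. A reader might infer that an arm could look less suicidal overall, or that a harm signal would be hidden. The documents do not support that.

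Second, the SAP is silent on blanks. It does not prescribe recorded-only averaging, and scoring no ideation as type 0 is compatible with its text and removes the reversal for that item. This stands for ideation type. It does not help items on which 0 has another meaning, and for type itself the silence lets two programmers produce tables that point in opposite directions.

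Three further readings are tempting and carry no weight.

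- Injurious attempts might seem lost because potential lethality excludes them. They are scored under actual lethality, which the same sentence of the SAP summarises.
- Taking each item's extreme across visits can pair values from different episodes. As a marginal summary of each item that is defensible, and the SAP does not claim that they come from one visit.
- Neither appended form has a total score, so the model in Protocol 13.4 could not be run as worded. The SAP's precedence rule already settles this.

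Finally, 3.9.2 attaches no test or decision to these means.

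**Conclusion.** The point holds as a minor defect in a descriptive table. SAP 3.9.2 plans arm means for ordinal items that exist only for participants selected by the outcome, and it states neither the population nor a rule for blanks. With 40 per arm and assumed counts, mean ideation severity can fall from 4.0 to 2.1 while the proportion with any ideation rises from 5% to 20%.

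That reversal rests on two conditions: only recorded scores are averaged, and the existing cases are more severe than the added ones. It follows from the ideation skip rule; the potential-lethality rule is a smaller, separate matter of labelling. Incidence is correctly planned, so what is at risk is the severity comparison, not detection of the signal.

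**What to change.** In SAP 3.9.2, with the matching entries in 3.2.2:

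- **Most severe ideation.** Replace the arm summary with the number and percentage in each category from 0 (no ideation) to 5 by arm, over the ST sample, with a row for participants not assessed.
- **Intensity items.** Show category counts by arm, labelled as among participants with ideation, with n. Do not fill blanks with 0. State that minimal controllability and minimal deterrents mean the worst state, that is the higher codes, with code 0 shown separately.
- **Lethality.** List each actual attempt with its actual lethality, and give potential lethality only as a sub-code where actual lethality is 0.

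Deleting the total-score sentence from Protocol 13.4 is optional housekeeping.

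The cost is a few lines of SAP text and a different table layout. No new data are needed. What is lost is a one-line mean per item.

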### 3.2.2 Safety Endpoints

The following safety endpoints will be evaluated:

- Proportion of participants experiencing and number of unique events of each type of TEAE and serious TEAE classified by MedDRA system organ class and preferred term,
- Proportion of participants experiencing and number of unique events of TEAEs classified by seriousness, severity, relatedness to study drug, relatedness to TMS and TTNCS procedures, action taken with study drug, action taken with TMS/TTNCS, and outcome, summarized across all MedDRA terms,
- Instances of treatment-emergent laboratory abnormalities classified by assay, whether the abnormality is below or above the normal range, and extend of deviation from normal,
- Mean change from baseline in weight
- Proportion of participants experiencing treatment-emergent clinically significant ECG abnormalities
- Proportion of participants experiencing treatment-emergent ophthalmologic complication,
- Mean change in AUA Symptom Score and proportion of participants with mild, moderate, or severe symptoms by visit,
- Proportion of participants reporting any treatment-emergent suicidal ideation
- Maximum post-baseline suicidal ideation planning, frequency, duration, controllability, deterrents, and reasons
- Proportion of participants reporting any post-baseline suicidal behavior, actual attempts, non-suicidal self-injurious behavior, interrupted attempts, aborted attempts, preparatory acts or behaviors, or completed suicide
- Maximum post-baseline suicidal behavior lethality and potential lethality

Reported proportions will use as their denominator all participants in the Safety and Tolerability sample (see Section 3.5 below).

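### SAP 3.9.2 lists non-suicidal self-injury among the suicidal behaviors, against the wording of the appended C-SSRS; the composite needs a corrected definition (minor)

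*Protocol*

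**What the plan says.** SAP 3.9.2 sets out the summary: "The proportion of participants who report any post-baseline suicidal ideation or any post-baseline suicidal behavior will be summarized by treatment group". The next sentence says what the term covers: "Suicidal behaviors will include: actual attempts, non-suicidal self-injurious behavior, interrupted attempts, aborted attempts, preparatory acts or behaviors, and completed suicide". No other text in either document says which categories make up the any-behavior row.

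SAP 3.2.2 gives the endpoint as "Proportion of participants reporting any post-baseline suicidal behavior, actual attempts, non-suicidal self-injurious behavior, interrupted attempts, aborted attempts" and goes on to preparatory acts and completed suicide. The overall proportion comes first and each category follows. The denominator is the Safety and Tolerability sample.

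The form for follow-up visits is in Protocol 16.4, Appendix IV. For an actual attempt it requires at least some wish to die. The last probe under that item, "Or did you do it purely for other reasons / without ANY intention of killing yourself", is labelled "Self-Injurious Behavior without suicidal intent", and the answer goes into a Yes/No box of its own. Further down, a separate Yes/No item asks whether "Suicidal behavior was present during the assessment period".

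SAP section 1 makes the SAP prevail over the protocol on matters of analysis, so the appendix does not override SAP 3.9.2.

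**The concern.** A programmer who follows SAP 3.9.2 literally would flag a participant whose only event is self-injury with no intent to die as having suicidal behavior. On the form, the same participant could be a No on the overall suicidal-behavior item. The table and the source record would then disagree, and neither document explains why.

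Suicidality is a named safety outcome (Protocol 3.2.2; SAP 2.2). Protocol 2.3.1.1 cites about a two-fold increase in suicide risk from pooled analyses of anti-epileptic drugs. Protocol 13.4 had planned a mixed-model analysis of C-SSRS total scores, whereas SAP 3.9.2 plans descriptive summaries only. Readers will therefore compare the arms on these proportions and the accompanying severity summaries. Where events are rare, one participant counted under the wrong label can account for all of an apparent difference.

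**Working it through.** The plan states no expected rate, power or threshold for suicidality, so there is no figure to reproduce. The check is a comparison of definitions, followed by a simple sizing.

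**Step 1: the six SAP categories against the form (Protocol 16.4).**

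- Actual attempt: needs some wish to die.
- Interrupted attempt: an actual attempt would have followed but for an outside circumstance.
- Aborted attempt: steps toward a suicide attempt, halted by the person.
- Preparatory acts or behavior: preparation for an imminent suicide attempt.
- Completed suicide: its own Yes/No item.
- Non-suicidal self-injurious behavior: defined by the absence of suicidal intent.

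Five of the six categories refer to suicide or a suicide attempt. The sixth is defined by excluding it.

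**Step 2: effect on the reported proportion.** Let n be the arm size, S the number of participants with one of the other five behaviors, and k the number with non-suicidal self-injury and none of the five.

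- Proportion under SAP 3.9.2 as written: (S + k)/n
- Proportion without non-suicidal self-injury: S/n
- Difference: k/n

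Input: n = 40 per arm (SAP 3.4). A value of n = 30, which is 40 × (1 − 0.25), is shown only as a smaller arm for comparison, because SAP 3.7 reports slow enrollment and gives no final arm size.

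- n = 40, k = 1: 1/40 = 2.5 percentage points
- n = 30, k = 1: 1/30 = 3.3 percentage points
- k = 0: no difference at any n
- Example with n = 40, S = 0, k = 1: 2.5% as written, 0.0% after correction

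Within an arm the proportion can only go up. The difference between arms can move either way, depending on where the cases fall.

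**Step 3: how likely is k of at least 1?** The documents give no rate, so the rates p below are assumptions. The formula is 1 − (1 − p)^n.

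| Assumed rate p | One arm, n = 40 | All arms, n = 120 |
|---|---|---|
| 0.5% | 18% | 45% |
| 1% | 33% | 70% |
| 2% | 55% | 91% |

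The table shows only that a case is possible at low rates. It is not a forecast.

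**The case against.** The strongest reply is that the SAP follows the form. The form prints the non-suicidal item inside its Suicidal Behavior section, which tells the interviewer to ask about all types, and the SAP list keeps the form's printed order. The sentence in SAP 3.9.2 may be a list of rows to tabulate. It does not say outright that the any-behavior row is the union of the six items, and the form's own overall item could supply that row. SAP 3.2.2 lists each category, so a reader would normally see when an overall count comes from non-suicidal self-injury. No test, alpha or stopping rule is attached.

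Much of this stands, and it limits the point. It does not remove it. Position under a heading does not settle meaning when the item's own wording excludes suicidal intent. The sentence directly after the planned proportion calls the item a suicidal behavior, and no other text gives a different rule.

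Three stronger readings are tempting but not supported:

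- A reader might infer that the reported proportion is bound to be wrong. It differs only if someone has non-suicidal self-injury and none of the other listed behaviors.
- A reader might treat this composite as the plan's main suicidality result. Neither document ranks it so.
- A reader might argue that a real signal would be diluted: with 3/40 against 1/40, adding two cases per arm gives 5/40 against 3/40, and the ratio falls from 3.0 to 1.67. Those counts are invented. The SAP reports proportions, and the difference is 5.0 points both before (7.5% − 2.5%) and after (12.5% − 7.5%).

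**Conclusion.** The point holds as a minor error of definition in SAP 3.9.2. As written, the section classes as suicidal a behavior that the trial's own instrument describes as lacking suicidal intent, and SAP 3.2.2 does not say which categories form the overall row. The form in Appendix IV needs no change.

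The size is 2.5 percentage points per affected participant, assuming the planned 40 per arm. The number of such participants cannot be derived from the documents and may be zero. The conclusion assumes that the any-behavior row would be programmed from the list in SAP 3.9.2. If it were taken from the form's overall item instead, the remaining fault would be that the SAP does not say so. Severity is minor because the summary is descriptive, nothing is decided on it, and the component is collected and listed separately.

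**What to change.** - In SAP 3.9.2, define any suicidal behavior as an actual, interrupted or aborted attempt, preparatory acts or behavior, or completed suicide.
- Take non-suicidal self-injurious behavior out of that list and report it by arm on its own line.
- In SAP 3.2.2, state the same composite and keep non-suicidal self-injury as a separate entry.

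The cost is a sentence or two in the SAP and one table row. The form already records the item in its own box, so no new data are needed and no information is lost.
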